14.0 BIOSTATISTICS

14.1 Primary and Secondary Endpoints Statistical Considerations

The primary objective is to evaluate the efficacy, as assessed by the best objective response rate (complete response + partial response) at 24 weeks by RECIST 1.1 (primary endpoint; Phase II). The study will use a one stage design based on the exact binomial test. A 5% response rate will be considered not promising,^{94,95} a 30% response rate will be considered promising. There will be a maximum accrual of 20 patients to this study, with early stopping rules for predefined treatment-related toxicities. . It will be concluded that the true response rate is $> 5\%$ if there are 3 or more patients with an objective response among 20 patients. The design has a type I error rate of 0.08 and a type II error rate of 0.04. This design provides 96% probability of a positive result if the true response rate is at least 30%, and a 92% probability of a negative result if the true response rate is 5% or lower.

The patient population in this study represents patients with locally advanced/metastatic sarcoma that have received at least one line of previous therapy. The references supporting the 5% null rate include the PALETTE, double-blind, randomized placebo-controlled trial⁹⁴ and a study looking at the efficacy of eribulin in patients with advanced

sarcoma.⁹⁵ The PALETTE study compared pazopanib with placebo in patients with least one regimen containing an anthracycline and a maximum of four previous lines of systemic therapy for metastatic disease (no more than two lines of combination regimens). The response rate for pazopanib was 6% in this study. Pazopanib was granted FDA approval for advanced sarcoma patients that have previously received chemotherapy on the basis of this study which showed an improvement in PFS favoring pazopanib. The second reference refers to a randomized phase 3 study that compared eribulin with dacarbazine in patients with advanced leiomyosarcoma and liposarcoma that have progressed on two previous lines of therapy including an anthracycline. In this study the proportion of patients who had an objective response did not differ between treatment groups (nine [4%] in the eribulin group vs 11 [5%] in the dacarbazine group; $p=0.62$). Dacarbazine is FDA approved for advanced sarcoma and eribulin obtained FDA approval for use in advanced liposarcoma on the basis of this study. Hence, a 5% response rate has been seen with standard chemotherapy agents approved in this patient population. Therefore, in assessing the efficacy of a new therapy in this study population a response rate of $> 5\%$ would be preferred to determine the therapy as having a signal of efficacy.

Secondary endpoints include:

1. Feasibility of the combination of talimogene laherparepvec and pembrolizumab in patients with locally advanced or metastatic sarcoma and early-stopping rules

In order to account for unexpected toxicity of the treatment, we will implement an early stopping rule for sequential toxicity monitoring. The results of the previous phase I trial that examined the safety of this combination of drugs reported that all 21 patients in the study experienced a treatment-related adverse event. The treatment related adverse event rate was 19%; G3 treatment related adverse event rate was 29%, there were no G4 treatment related adverse events. However, the rate discontinuation of study therapy due to treatment related adverse events in the phase I study was 0%.⁹¹ This phase II study will be deemed feasible if the primary objective of efficacy of the combination therapy is determined without crossing a boundary that requires early stopping.

The number of patients who experience pre-specified treatment-related toxicity events detailed as per section 11.1.1, that result in the discontinuation of the study drug(s) or delay of their administration ≥ 9 weeks from the planned date of study drug(s) administration, will be recorded. Early stopping rules will be defined such that a 10% rate of occurrence of the above drug-related toxicities is acceptable, whereas a 30% rate would be unacceptable. The study will be continuously monitored for drug-related toxicity events that result in the discontinuation of the study drug(s) or delay of their administration ≥ 9 weeks from the planned date of study drug(s) administration. Early stopping rules are defined as observing such events in 2/4, 3/8, 4/14 or 5/20 patients. The probability of stopping under this rule is approximately 10% if the true treatment related toxicity event rate (that results in treatment discontinuation or delay in treatment administration ≥ 9 weeks) is 10%, and is approximately 79% if the true treatment related toxicity event rate (that results in treatment discontinuation or delay in treatment administration ≥ 9 weeks) is 30%. Enrollment will not pause, treatment

related toxicity events will be continuously monitored and the study terminated immediately if the pre-defined early-stopping rule boundary is crossed.

2. Toxicity

Adverse events will be graded according to the NCI CTCAE v4.03, presented on an individual basis and summarized using descriptive statistics.

3. Survival

Progression free survival (PFS) rate at 24 weeks, median PFS, overall survival (OS) Overall and progression-free survival intervals will be estimated using Kaplan-Meier methodology

4. Best Objective Response by irRECIST

Best objective response rate (complete response + partial response) at 24 weeks by immune-related Response Evaluation Criteria in Solid Tumors (irRECIST), of talimogene laherparepvec in combination with pembrolizumab in patients with metastatic and/or locally advanced sarcoma.

Descriptive statistics will be provided for demographics, safety, efficacy, and biomarkers as appropriate. Patients who have not experienced the event of interest by the end of the study will be censored at the time of the last follow-up.

Due to the small sample size, the correlative studies using tumor biopsies will be exploratory and hypothesis generating in nature.

Patients evaluable for efficacy analysis will include all patients treated with talimogene laherparepvec or pembrolizumab and assessable for response. Patients who are missing an assessment of response post baseline will not be considered evaluable for response unless they missed the assessment due to progression of disease in which case they will be considered non-responders for that time point. Patients who miss an assessment of response post baseline for any reason other than progression of disease will be replaced.

Patients evaluable for safety analysis will include all patients who have received at least one dose of talimogene laherparepvec and pembrolizumab.

We expect to accrue approximately 1-2 patients each month and hence expect to finish enrollment in 10-20 months.

Additional cohorts:

Locally advanced/metastatic cohorts:

Primary End Point

The primary objective is to evaluate the efficacy of the combination therapy in each subtype-specific cohort, as assessed by the best objective response rate (complete response + partial response). The primary endpoint is best objective response rate (RECIST 1.1). It will be estimated for each subtype-specific cohort, as the proportion of evaluable patients who have complete response and partial response as defined by RECIST 1.1 criteria, with a two

sided 95% CI provided. The lower limit of the CI allowed by a sample size of 10 is provided for a range of possible ORR in the below table.

Table 15. 95% CI for estimating ORR for a Sample Size of 10 Patients

Estimated ORR	0.20	0.30	0.40	0.50
CI 95%	0.03~0.56	0.07~0.65	0.12~0.74	0.19~0.81

Patients evaluable for efficacy analysis will include all patients who have received at least one cycle of treatment with T-VEC and pembrolizumab and are assessable for response. Patients who are missing an assessment of response post baseline will not be considered evaluable for response unless they missed the assessment due to progression of disease or treatment related toxicities in which case they will be considered non-responders for that time point. Patients who miss an assessment of response post baseline for any reason other than progression of disease and treatment related toxicity will be replaced.

In relation to the design of the additional locally advanced/metastatic cohorts, there will be 3 histology specific groups: i) cutaneous angiosarcoma, ii) epithelioid sarcoma, and iii) undifferentiated pleomorphic sarcoma/myxofibrosarcoma. These sarcoma subtypes reflect the subtypes where clinical activity was demonstrated in the phase II study to date.

We expect to accrue approximately 1-2 patients each month and hence expect to finish enrollment in 15-30 months.

Secondary endpoints

1. Safety

Patients evaluable for safety analysis will include all patients who have received at least one dose of T-VEC and pembrolizumab. Adverse events will be graded according to the NCI CTCAE v4.03, presented on an individual basis and summarized using descriptive statistics.

2. Survival

Progression free survival (PFS) rate at 24 weeks, median PFS, overall survival (OS) and progression-free survival intervals will be estimated using Kaplan-Meier methodology

3. Best Objective Response Rate by irRECIST

Best objective response rate (complete response + partial response) by 24 weeks by immune-related response criteria (irRECIST), of T-VEC in combination with pembrolizumab in patients with metastatic and/or locally advanced, sarcoma.

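### The 96% probability of a positive result belongs to the 3-of-20 efficacy rule alone; with the toxicity stop in the same design it is about 86–90% on the plan's own stopping probability

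*Combined protocol and SAP*

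**What the plan says.** Section 14.1 sets out the efficacy design and the toxicity rule together. On efficacy: "The study will use a one stage design based on the exact binomial test". A 5% response rate is not promising, and "a 30% response rate will be considered promising". On size: "There will be a maximum accrual of 20 patients to this study, with early stopping rules for predefined treatment-related toxicities". A response rate above 5% is concluded "if there are 3 or more patients with an objective response among 20 patients". The section continues: "The design has a type I error rate of 0.08 and a type II error rate of 0.04", and then: "This design provides 96% probability of a positive result if the true response rate is at least 30" per cent. It gives a matching 92% probability of a negative result at a response rate of 5% or lower.

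Under the feasibility endpoint in the same section, the study stops if qualifying toxicity events are seen in 2/4, 3/8, 4/14 or 5/20 patients. A 10% event rate is acceptable and a 30% rate is not. "The probability of stopping under this rule is approximately 10% if the true treatment related toxicity event rate" is 10%, and about 79% if it is 30%. Enrolment does not pause, and treatment "related toxicity events will be continuously monitored and the study terminated immediately if the pre-defined early-stopping rule boundary is crossed".

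The section gives no combined probability. It does not say that the 96% is conditional on no toxicity stop, nor how efficacy is judged if the study stops early.

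**The concern.** The sentence with the 96% attributes it to the design, and the design as described in that paragraph includes the toxicity stop. The success rule needs 20 patients. If about one study in ten is terminated even at acceptable toxicity, a 20-patient success rule cannot succeed 96% of the time in that design. A reader planning from this section, or quoting it in a report, would take 96% as the chance that an active and acceptably tolerated combination yields a positive result. That chance is lower. How much lower depends on two things that section 14.1 leaves open: whether responses already seen at a toxicity stop count, and how quickly toxicity events come to light.

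**Working it through.** **Inputs, all from section 14.1.** N = 20; success at 3 or more responses; response rates 5% and 30%; toxicity boundary 2/4, 3/8, 4/14, 5/20; acceptable and unacceptable toxicity rates 10% and 30%.

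**Step 1: reproduce the stated efficacy figures, with no toxicity stop.**
- P(X ≥ 3 | 20, 0.30) = 0.9645; the plan says 96%.
- P(X ≤ 2 | 20, 0.30) = 0.0355; the plan says 0.04.
- P(X ≥ 3 | 20, 0.05) = 0.0755; the plan says 0.08.

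All three agree after rounding, so the stated error rates are those of the efficacy rule alone.

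**Step 2: reproduce the stated stopping probabilities.** Exact patient-by-patient recursion, stopping at 2 events within the first 4 patients, 3 within 8, 4 within 14 or 5 within 20:

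| Toxicity rate | Cross at any point | Cross before patient 20 | Plan |
|---|---|---|---|
| 10% | 0.104 | 0.099 | about 10% |
| 30% | 0.816 | 0.788 | about 79% |

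The plan's figures match crossing before patient 20, so the boundary is being read as the plan reads it.

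**Step 3: combine the two at 30% response and 10% toxicity.** Assume that response and toxicity are independent and that each patient's toxicity status is known as the patient is counted.
- Any crossing prevents a positive result: 0.9645 × (1 − 0.104) = 0.864.
- Only a crossing before patient 20 prevents it: 0.9645 × (1 − 0.099) = 0.869.
- A stopped study counts as positive with 3 or more responses among those enrolled at the stop: add the sum over n of P(stop at n) × P(X ≥ 3 | n, 0.30) = 0.038, giving 0.864 + 0.038 = 0.902.

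**Step 4: relax independence.** For the strictest scoring, the joint probability must lie between 0.9645 + 0.896 − 1 = 0.861 and min(0.9645, 0.896) = 0.896, whatever the dependence.

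**Step 5: relax immediate toxicity.** If every event surfaced only after all 20 were enrolled, just the 5/20 boundary would apply. P(5 or more events in 20 at 10%) = 0.043, so the strict figure is 0.9645 × (1 − 0.043) = 0.923. It is 0.9645 if the 20 patients' responses count regardless. Between these extremes, simulation used accrual of 1–2 patients a month (section 14.1) and event times spread evenly over the first 3 to 12 months after entry (an assumption). It gives roughly 89–92% under strict scoring and 93–96% with responses credited, moving by about a point with how entry times are modelled.

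**Step 6: false positives.** At 5% response and 10% toxicity, on the Step 3 assumptions, the rate is 0.0755 × 0.896 = 0.068, or 0.069 with responses credited, against the stated 0.08.

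**The case against.** The strongest reply is that no stated number is miscalculated. The section names a one-stage exact binomial test, conditions its probabilities on response rate only, and reports the toxicity rule's properties separately under feasibility. Reporting the two sets separately is common, and a reader can combine them approximately. This stands as far as the arithmetic goes. What is missing is a condition on the 96%, and that sentence refers to a design whose description includes the toxicity stop.

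A second reply is that 86–90% needs toxicity to be known almost at once. The plan points the other way: section 11.1.1 counts events throughout the study period and includes dosing delays of more than 9 weeks, and enrolment does not pause. This also stands. It is why the timing assumption must be stated beside any combined figure, and why 90% is not a hard upper limit.

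A third reply concerns an inference that a reader might draw, that the type II error is really about 0.14, or several times the stated 0.04. The documents do not support it. Type II error here is failing to conclude that response exceeds 5%; stopping for toxicity is a separate decision, which the plan ties to feasibility. Nor should the low success probabilities at 30% toxicity be read as lost power, because stopping at that rate is what the rule is for.

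Finally, little now depends on the figure. Section 4.1 reports a 24-week response rate of 30% in the first 20 patients, which is 6 of 20 against a threshold of 3, and the additional cohorts use estimation with confidence intervals, not this test.

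**Conclusion.** The point holds as one of labelling and completeness. The 96%, 92%, 0.08 and 0.04 are correct for the 3-of-20 rule when the toxicity boundary is not crossed, and the section presents them as unconditional properties of a design that can also stop for toxicity.

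At 30% response and the acceptable 10% toxicity rate, the overall probability of a positive result is about 86–87%, or about 90% with responses at the stop credited. That is a shortfall of 6 to 10 points from 96%. It rests on independence of response and toxicity and on toxicity being known as each patient is counted. Dependence changes the strict figure little; late-emerging toxicity narrows the shortfall to between about 4 points and none.

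A reader might also infer that the false-positive risk is understated. It is not: at 10% toxicity it falls to about 7%. The result already reported for the first 20 patients is not put in doubt.

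**What to change.** In section 14.1:
1. Label 0.08/0.04 and 92%/96% as the error rates and probabilities of the efficacy rule when the toxicity boundary is not crossed.
2. Add the overall probability of a positive result at 30% response and 10% toxicity: about 86–90% using the plan's own stopping probability, with the assumptions of independence and toxicity timing stated, and a note that it rises toward 92–96% if events emerge late.
3. State whether 3 or more responses already seen when the toxicity boundary is crossed count as a positive efficacy result.

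Leave the type II error of the efficacy rule at 0.04.

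The cost is two or three sentences. The stated probability of success becomes less favourable. Sample size, success threshold and toxicity boundaries do not change.

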10.0 EVALUATION DURING TREATMENT/INTERVENTION

10.1 – Pre-treatment diagnosis confirmation

All patients will have histological confirmation of their diagnosis prior to treatment. Baseline clinical and radiologic evaluations are to be conducted within 3 weeks of starting protocol therapy. In addition, a mandatory baseline biopsy will be performed within 30 days of first dose of the study drugs for all patients enrolled in the study where feasible.

10.2 – Standard evaluations

Locally advanced/metastatic cohort

Evaluations at clinic visits will occur at weeks 1 and 4 (\pm 3 days), and then prior to every scheduled treatment (\pm 3 days) thereafter. Patients who achieve response/stability of disease lasting for at least 12 months and come off study therapy will be followed every 2 months (\pm 2 weeks) thereafter. Imaging studies will be performed at baseline, week 8 and every 8 weeks subsequently (\pm 1 week window) until 56 weeks, and then every 12 weeks thereafter or as per the discretion of the treating investigator. The clinical evaluations are delineated further in the study calendar (Table 6) and include:

- Full medical history, physical exam, assessment of performance status by KPS or ECOG status
- Review of concomitant medications
- Complete vital signs (pulse, blood pressure, temperature, respiratory rate) as well as weight and height. Height may be documented at any time prior to registration.

All patients will undergo a baseline staging CT scan of the chest (with or without contrast), abdomen and pelvis (with contrast where renal function permits), and MRI abdomen/pelvis (with and without contrast) if deemed necessary by the treating physician. Response evaluations will occur at week 8 and every 8 weeks subsequently (\pm 1 week window) until 56 weeks, and then every 12 weeks thereafter or as per the discretion of the treating investigator. EKGs will also be performed at baseline, week 8 and every 8 weeks thereafter to evaluate the heart during the study.

Routine/standard blood samples will be obtained at screening, weeks 1, 4 and then prior to every scheduled treatment (\pm 3 days) thereafter. All routine blood samples should be obtained prior to the daily dose talimogene laherparepvec and/or pembrolizumab. These samples will be used for routine tests and are part of standard of care. The following analyses will be assessed at various time points during the study:

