12.10 Progression-Free Survival (PFS)

PFS is defined as the period from start of study treatment until recurrent or progressive of disease (POD) is objectively documented (taking as reference for progressive disease the smallest measurement recorded on study), death, or date of last evaluable tumor assessment

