12.11 Overall Survival (OS)

OS is defined as the observed length of life from start of study treatment to death or the date of last contact.

12.12 Secondary Response Criteria – Modified immune-related response evaluation Criteria in Solid (irRECIST)

Immune related RECIST (irRECIST)

In 2013, Nishino et al. demonstrated that immune-related response criteria using unidimensional measurements were highly concordant with the bidimensional results of irRC, but with less measurement variability. Based on these findings and in order to utilize

both the established criteria of irRC and RECIST 1.1, the two systems have been adapted, modified, and combined into the Immune-related Response Evaluation Criteria in Solid Tumors (irRECIST). The adapted irRECIST criteria are modifications to the irRC, incorporating the findings of Nishino et al. and the advantages of RECIST 1.1 while overcoming the shortcomings of each of the other guidelines.

irRECIST

Immune-related RECIST (irRECIST) guidelines according to Bohnsack et al. are presented below.

I. Baseline Assessments in irRECIST

In irRECIST, baseline assessment and measurement of measurable/non-measurable and target/non-target lesions and lymph nodes are in line with RECIST 1.1.

One new definition is added: If a subject has no measurable and no non-measurable disease at baseline the radiologist will assign 'No Disease' (irND) as the overall tumor assessment for any available follow-up time points unless new measurable lesions are identified and contribute to the total measured tumor burden (TMTB). irND is a valid assessment in studies with adjuvant setting where the protocol and study design allow the inclusion of subjects with no visible disease

Follow-up Assessments in irRECIST

A. Follow-up recording of target and new measurable lesions

The key difference in irRECIST is that the appearance of new lesions does not automatically indicate progression. Instead, all measured lesions (baseline-selected target lesions and new measurable lesions) are combined into the total measured tumor burden (TMTB) at follow up. Baseline-selected target lesions and new measurable lesions are NOT assessed separately. Measurements of those lesions are combined into the TMTB, and one combined assessment provided.

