Due to the mechanism of action, subjects may experience growth in existing tumors or the appearance of new tumors prior to maximal clinical benefit of talimogene laherparepvec and pembrolizumab. The patient may be allowed to continue study treatment after initial RECIST 1.1 defined progression if they are assessed by the treating physician to be deriving clinical benefit and tolerating study treatment. The treating physician may consult with the overall study PI for help with assessing the patient. Such patients should discontinue study therapy upon further evidence of progression.

Safety follows up and End of Study visit

Upon permanent discontinuation from the study treatment for any reason, the following procedures will be performed approximately 30 (+7) days after the last dose of talimogene laherparepvec or the last dose of pembrolizumab, whichever is later in patients with metastatic or locally advanced sarcoma.

- Full medical history, physical exam, assessment of performance status by KPS or ECOG status
- Review of concomitant medications
- Complete vital signs (pulse, blood pressure, temperature, respiratory rate) as well as weight and height. Height may be documented at any time prior to registration.
- 12-lead electrocardiogram (EKG)
- Serum β -HCG pregnancy test for women with child-bearing potential. Complete blood count with differential, including lymphocyte and eosinophil count.

- Comprehensive metabolic panel (glucose, blood urea nitrogen, creatinine, sodium, potassium, chloride, bicarbonate, calcium, total protein, albumin, serum bilirubin, alkaline phosphatase, ASL, AST, phosphorus, magnesium, TSH, T4 free).
- Amylase and lipase
- An optional biopsy will be offered at progression of disease.

Patients whose treatment is interrupted or permanently discontinued due to an adverse event or clinically significant laboratory value must be followed until resolution or stabilization of the event.

Reporting of adverse events will occur for up to 30 days for serious adverse events (within 30 [+7] days after the last administration of talimogene laherparepvec or pembrolizumab, whichever is later), Events of Clinical Interest (within 30 [+7] days after the last administration of talimogene laherparepvec or pembrolizumab, whichever is later), and documentation of concomitant medications. In the neoadjuvant cohort, reporting of serious adverse events will occur for up to 30 days from the date of surgical resection.

Long-Term Follow-up Procedures:

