
All subjects who permanently discontinue study drug for any reason other than withdrawal of full consent will be contacted by clinic visit or telephone to assess survival and initiation of additional sarcoma therapy. Contact for all subjects will be attempted every 12 weeks (\pm 14 days) following the safety follow-up visit until death, subject withdraws full consent, or up to 12 months after the end of treatment for patients with metastatic or locally advanced sarcoma and for up to 36 months after the completion of surgery for recurrent, operable sarcoma. If patients do not proceed to surgical resection upon conclusion of study therapy, patients will be followed with interval scanning and clinical surveillance every 6-8 weeks for one year or until completion of participation on study.

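### Does the generic censoring sentence in section 14.1 leave the PFS censoring date open and inflate 24-week PFS?

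*Combined protocol and SAP*

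**What the plan says.** Section 14.1, in the descriptive-statistics paragraph for the initial 20 patients, states that those who have not had the "event of interest by the end of the study will be censored at the time of the last follow-up". No endpoint is named and the date is not defined.

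The endpoint definitions stand in section 12. Under 12.10, PFS runs from the start of treatment to objectively documented progression, "death, or date of last evaluable tumor assessment". Under 12.11, overall survival (OS) is the "observed length of life from start of study treatment to death or the date of last contact".

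For the added histology cohorts, section 14.1 says only that "overall survival (OS) and progression-free survival intervals will be estimated using Kaplan-Meier methodology", with no censoring rule of its own.

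On follow-up, section 10.2 states: "Imaging studies will be performed at baseline, week 8 and every 8 weeks subsequently". Section 13.0 says of the off-study visit that "the following procedures will be performed approximately 30 (+7) days after the last dose of talimogene laherparepvec or the last dose of pembrolizumab"; its list contains no scan. After that, patients who have stopped the drug "will be contacted by clinic visit or telephone to assess survival and initiation of additional sarcoma therapy", every 12 weeks for up to 12 months.

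**The concern.** Last follow-up and last evaluable scan can be different dates. A patient could stop treatment without documented progression, have no further scan, and still attend the off-study visit or answer a call months later. Censoring PFS at that later contact keeps the patient in the risk set at scan times when nobody looked for progression.

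The effect has one direction. Each Kaplan-Meier factor is 1 − d/n, where d is the number of events and n the number at risk. A later censoring date raises n and leaves d alone, so the estimate stays equal or rises. The 24-week PFS rate is a named secondary objective, and two analysts using different sentences of the same document could report different values. The one working from 14.1 alone would report the higher or equal value.

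**Working it through.** **1. Does the plan supply a date?** The sections compare as follows.

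| Endpoint | Section 12 | Section 14.1 |
|---|---|---|
| PFS, initial 20 | last evaluable tumor assessment (12.10) | last follow-up, endpoint not named |
| OS, initial 20 | last contact (12.11) | last follow-up, endpoint not named |
| PFS and OS, added cohorts | same definitions | no rule stated |

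The 14.1 sentence speaks of the event of interest, which changes with the endpoint. Read that way, follow-up for progression ends at the last tumor assessment and follow-up for death at the last contact, as 12.10 and 12.11 say. In the added cohorts, section 12 is the only source. Nothing suggests that the same definition applies there but not to the first 20 patients.

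**2. Who would be affected by the literal reading?** For 24-week PFS, only a patient who stops scanning before week 24, has neither progression nor death, and has a contact on or after a later scan time at which others progress. Several provisions shrink that group:

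- The 8-weekly imaging in 10.2 is not expressly ended when the drug stops.
- Section 4.1 keeps patients who complete the study in response on 12-weekly imaging until confirmed progression.
- Section 4.1 describes survival contacts for patients with confirmed progression, who already have a PFS event. Section 13.0 is broader and covers everyone who stops the drug.
- Sections 12.3.1.3 and 12.7 ask for every effort to document objective progression after symptomatic deterioration.
- Sections 13.0 and 14.1 state: "Patients who miss an assessment of response post baseline for any reason other than progression of disease will be replaced". The text does not say whether this reaches the PFS set or a patient who already has one scan.

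The group may be empty.

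**3. How large would the effect be?** The plan gives no figure that depends on the PFS censoring date, so there is none to reproduce. The event counts below are assumptions. Take 20 patients with progression in 5, 3 and 2 at weeks 8, 16 and 24.

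- Literal reading, contact after week 24: 15/20 × 12/15 × 10/12 = 50.0%.
- Censored at a week-8 scan, one patient: 15/20 × 11/14 × 9/11 = 48.2%.
- Censored at a week-8 scan, two patients: 15/20 × 10/13 × 8/10 = 46.2%.
- Censored at a week-16 scan, one patient: 15/20 × 12/15 × 9/11 = 49.1%.
- Censored at a week-16 scan, two patients: 15/20 × 12/15 × 8/10 = 48.0%.

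The literal reading is therefore 0.9 to 3.8 points higher. The exact 95% interval for 10 of 20 is 27% to 73%.

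If the sentence were carried over to a cohort of 10 with progression in 3, 1 and 1, the literal reading gives 7/10 × 6/7 × 5/6 = 50.0%. Censoring one patient at a week-8 scan gives 7/10 × 5/6 × 4/5 = 46.7%, a gap of 3.3 points.

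**4. How firm is that size?** Simulations with 20 patients and a true 24-week PFS of 40% show how far it depends on assumptions. If 5%, 10% or 20% stop scans at times spread over weeks 8 to 52, the mean rise is 0.4, 0.9 or 1.8 points. If the same shares are lost to imaging by week 24, it is 1.9, 3.7 or 7.4 points. That is about a fourfold difference between two assumed patterns of stopping, and the documents support neither. In the second set, censoring at the last scan gave mean estimates of 40.0% to 40.1%, so the 12.10 rule does its job when loss of imaging is unrelated to progression.

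**The case for a change.** The best case for a change is that the statistical section is where an analyst looks first, and its one censoring rule fits OS better than PFS. The dates can part under this protocol: neither the off-study procedures nor the later contacts include imaging. A patient taken off for clinical progression or symptomatic deterioration may have no objectively documented progression, and so no PFS event, yet remain in telephone contact. An effort to document progression does not guarantee a scan. The only possible error is favorable to the treatment, two affected patients matter more in a cohort of 10, and the remedy costs one sentence.

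What stands is that 14.1 does not refer back to 12.10 and 12.11, that the dates can differ, and that the direction is upward only. What does not stand is that the plan lacks the right date or prescribes a wrong one. The harm needs an analyst to set aside the protocol's only PFS definition in favor of a general sentence that does not mention PFS. The proposed sentence would restate 12.10 and 12.11 and add no rule. For patients who stop because they are deteriorating, the harder problem is that censoring at any date is informative, and restating the date does not cure that.

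**Conclusion.** No change is needed. This is a missing cross-reference that an analyst fills from section 12: PFS is censored at the last evaluable tumor assessment and OS at last contact, in all cohorts. On that reading the effect on 24-week PFS is zero.

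If 12.10 were ignored, the estimate could be equal or higher. The amount rests wholly on an assumed number and timing of patients who stop scans without progression. One or two such patients among 20 give 0.9 to 3.8 points in the worked example, and none gives zero. PFS is descriptive, with no null value, threshold or decision attached. The primary response-rate test and the toxicity stopping rule do not use it. Adding a pointer from 14.1 to 12.10 and 12.11 would be tidy, but it would not alter the analysis the plan already defines.
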